symptoms AND either a low thiamine biomarker or significant improvement in or resolution of symptoms of TD after receiving thiamine supplementation^{1,17,18}. Unfortunately, the available thiamine bioassays in the US (plasma thiamine or whole blood thiamine diphosphate (ThDP)) have reference ranges that are based on thiamine status in healthy individuals and have not been validated in those with clinical diagnoses of TDDs¹. In addition, there is uncertainty in interpreting biomarker results and a lack of consensus on which biomarker is superior at distinguishing TD⁴¹. Experts suggest that whole blood ThDP normalized to RBC volume or hemoglobin concentrations should be used to ensure data from different studies are comparable¹. Measuring serum and whole blood biomarkers concurrently would be important to validate each technique in the context of clinical TD that is responsive to replenishment. Filling the knowledge gap of clear case definitions of TDDs in non-alcohol using Veterans is an important step in achieving better outcomes with diagnosis and treatment.

Acute and chronic forms of inflammation may increase the risk of developing TD. It is accepted that inflammation is a significant risk factor for developing malnutrition^{42,43}. Acute and chronic forms of inflammation are thought to contribute to the development of malnutrition through associated anorexia. Decreased caloric intake in combination with elevated resting energy expenditure (which increases the need for thiamine as a metabolic co-factor) leads to a downward spiral of depleting thiamine stores in the face of reduced oral intake. Concomitant measurement of inflammatory markers and thiamine biomarkers combined with clinical evaluation of TDDs is an open question, the answer to which is needed to further our understanding of this condition in Veterans and to develop potential mitigation strategies.

Study Aims/Objectives:

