The **objective** of this proposal is to measure the prevalence of TD and TDDs in Veterans who don't use excessive alcohol and are ill enough to require hospitalization. Additionally, we will correlate biomarkers of thiamine with signs and symptoms of TDDs which improve with thiamine replenishment. Our central hypotheses are that the prevalence of TD in this population is as high as 25% based on reports of TD in various chronic disease states^{3,12,14,19–21,24–26}, and that TDDs reversible by replenishment may occur in the “low normal” range of blood thiamine levels^{14,44}. The rationale underlying this proposal is that failing to define the prevalence of TD in this population will perpetuate the current state of underdiagnosing and undertreating TDDs which contributes to loss of independence and function. If our hypothesis is correct that the prevalence is as high as 25%, filling this knowledge gap will increase awareness of and bring action to address these problems through practice change and improved health outcomes. A parallel problem faced is that there are currently no commonly accepted clinically relevant cut-points for TD biomarkers available in the US. Clarifying the “abnormally low” biomarker cutoff levels by comparing TDDs with measured blood thiamine levels will fill a knowledge gap that has been identified¹. Through carefully defining TDDs we will fill a critical knowledge gap and assist hospitalist and rehabilitation practitioners in making the diagnosis and implementing a treatment plan. Our **long-term goal** is to increase recognition and treatment of TDDs in Veterans by describing the clinical syndromes in non-alcoholics, as well as understand the root causes of TDDs. This will improve long-term health outcomes for Veterans with acute and chronic illnesses and help them maintain independence and function. We will test our central hypothesis and attain our objectives via the following **specific aims**:

Aim 1: Utilizing a prospective cohort study design, determine the prevalence of TD, as defined by whole blood and plasma thiamine levels and symptom responsive disease, and describe social and medical factors predisposing to TD in consecutively hospitalized non-alcoholic medicine patients.

Hypothesis 1: The prevalence of TD in hospitalized Veterans who do not use excessive alcohol is between 10 and 25%, much higher than the general population estimate of less than 3%.

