Aim 2: Through an open label treatment study, we will define thiamine deficiency disorders (TDDs) as cases with low or “low normal” thiamine levels and symptoms of TD that improve with thiamine replenishment. Hypothesis 2: The current bioassays of thiamine do not accurately define TDDs and individuals with results the “low normal” range will show symptom improvement with thiamine replacement.

Aim 3: Utilizing a nested case control study design, determine if acute and chronic inflammatory conditions with elevated biomarkers of inflammation increase the risk of developing TDDs. Hypothesis 3: Acute and chronic forms of inflammation cause oxidative stress which increase basal requirements for thiamine as a metabolic cofactor and increase the risk of developing TDDs.

Study Population:

We anticipate 300 patients will be enrolled in this study with an age range of 18 and older. There will be no exclusions due to gender, race, age, or ethnicity. We will endeavor to include women and minorities to the extent possible based on the inpatient population which historically has been predominantly male (95%) and white (90%). All subjects recruited for this study will be Veterans admitted to inpatient units at VA Sierra Nevada Healthcare System hospital (single site recruitment). There will be no minor children participating. The health status will be compromised from mild to severe due to the nature of being hospitalized. We will not include adults unable to consent (those who are cognitively impaired with Impaired Decision-Making Capacity). We will not enroll pregnant women as we do not admit them to the VA hospital due to lack of maternity services.

Inclusion criteria:

- anyone age 18 or older requiring full hospital admission to the medical service.

Exclusion criteria:

- excess alcohol intake as defined by the National Institute of Alcohol Abuse and Alcoholism as more than 14 standard drinks per week for men less than age 65, or more than 7 drinks per week for women or men 65 years of age or older
- unable to consent due to impaired decision making capacity.
- veterans who live more than 75 miles from the study site as that would likely hinder their ability to attend follow up visit 3.
- Veterans who suffer from quadriplegia because they cannot participate in the physical assessments
- Veterans taking thiamine supplements

Vulnerable Populations:

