10.3 Visit 3 – follow-up of symptomatic Veterans after empiric thiamine treatment. All Veterans with low biomarkers OR low normal biomarkers and clinical symptoms of TDDs that were initiated on replacement will be seen at a follow-up visit 3 after two weeks of thiamine replacement. We will repeat the symptom and function survey and repeat the standardized physical assessment. We will categorize changes in symptoms and signs as *no or minimal improvement, or noticeable improvement*. We will re-order thiamine biomarkers to assess for increases in levels. We will recommend continued dosing with thiamine 100 mg daily thereafter for any Veteran with improvement in their symptoms and update their medical record to include thiamine deficiency in their problem list. If a participant failed to complete the 2 weeks of replenishment, we will provide another 2-week course of replenishment and reschedule this visit.

Study Duration/ Study Timeline:

See Table 3. We expect visit 1 will not take substantial time for the Veteran. Visits 2 and 3 will take between 60 and 90 minutes each. For Veterans without symptoms of TD, their participation will be complete after visit 2, before discharge from the hospital. For Veterans with symptoms of TD their participation will be complete after taking thiamine for 2 weeks and attending visit 3. We anticipate the study will end 24 months.

Study Endpoints:

Our primary endpoint will be determining prevalence of TD in our Veteran population. We do not anticipate stopping the study before 300 Veterans are recruited. Thiamine supplements are very safe with few side effects, so we do not anticipate stopping early for safety concerns.

Study Locations:

The study will be conducted at the VA Sierra Nevada Healthcare System Hospital inpatient units at [name]. Follow up visits will occur on the ground floor of the hospital in the research department exam rooms.

International Research:

We will not be conducting this research in international locations.

Participant Compensation:

Those that agree to participate will be compensated \$30 for visits 1 and 2 and \$200 if they attend visit 3 after discharge.

Economic Burden to Participants:

Veterans will not incur any costs because of participating in this study. Those that attend the follow up visit will incur the cost of transportation, but this will be mitigated by the \$200 compensation.

Risk to Participants:

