Measurements: The **primary outcome** of this study is to measure the prevalence of TD as defined by abnormally low or low normal thiamine biomarkers combined with symptoms that respond to thiamine replenishment. **Secondary outcomes** will include describing demographic, clinical, and nutritional characteristics among those with and without TDDs. A TDD will be defined as an acute condition with symptoms that are known to be due to TD and that improve with adequate thiamine replenishment.

Statistical analysis/power calculations: Our primary endpoint is the prevalence of TDDs which we will compute as the proportion of TDD cases over the total number of subjects enrolled. Given the feasibility of this study and our patient population, we believe we can enroll and follow 300 subjects over a one-year enrollment period with an anticipated drop-out rate of 15%. Current best estimates for TD in similar populations are approximately 25%^{19,24,27}. Such an enrollment would provide us with a precision of TDD prevalence of +/- 5.4%. A sample size of 300 and estimated drop out of 15% leaving 255 subjects would provide us with 81% power to detect an 8% absolute difference from this expected prevalence. To explore differences in demographic, clinical, and nutritional characteristics among those with and without TDDs, continuous variables will be compared by T-test unless parametric assumptions are not met in which case a Kruskall-Wallis test will be used. Categorical variables will be evaluated through Chi-square or Fishers exact test depending on assumptions being met. We will estimate prevalence rate ratios for association factors. If the prevalence is achieved, we estimate that we would have adequate numbers to identify a range of different rates of exposure variables among TDD and non-TDD patients. For example, with 63 TDD and 192 non-TDD patients and a 10% rate of a given explanatory variable, we would have 80% power to detect prevalence rate ratios of ~2.5 and higher in bivariate analyses.

15.2 Open label treatment study to develop standardized case definitions of treatment responsive TDDs and correlate with thiamine biomarker levels to determine clinically relevant cut-points of those biomarkers.

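### Section 15.1 defines the primary prevalence both with and without a biomarker, so the case count can depend on which sentence is followed; exploratory Aim 3 has a lesser case-group mismatch.

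*Combined protocol and SAP*

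**What the plan says.** Section 15.1 (Measurements) sets the primary outcome as the "prevalence of TD as defined by abnormally low or low normal thiamine biomarkers combined with symptoms that respond to thiamine replenishment". Two sentences later it states: "A TDD will be defined as an acute condition with symptoms that are known to be due to TD and that improve" with adequate thiamine. No biomarker appears there. The statistical paragraph of 15.1 continues: "Our primary endpoint is the prevalence of TDDs which we will compute as the proportion of TDD cases", divided by all subjects enrolled.

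Other places use the two terms as follows.

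- Study Endpoints: "Our primary endpoint will be determining prevalence of TD in our Veteran population".
- Aim 1 is to "determine the prevalence of TD, as defined by whole blood and plasma thiamine levels and symptom responsive disease".
- Aim 2 will "define thiamine deficiency disorders (TDDs) as cases with low or “low normal” thiamine levels and symptoms of TD that improve" on thiamine, so TDD carries the biomarker here.
- The Background gives a third form of TD: "symptoms AND either a low thiamine biomarker or significant improvement in or resolution of symptoms of TD after receiving thiamine supplementation". No analysis refers to it.
- The planning text in 15.1 says "Current best estimates for TD in similar populations are approximately 25" per cent. It then gives a precision of ±5.4 points for TDD prevalence and an example with 63 TDD and 192 non-TDD patients.

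On who is assessed at visit 3, the body of section 10.3 requires a low or low-normal level. The heading of 10.3, Study Duration/Study Timeline, and Data and Specimen Banking refer to symptomatic Veterans on thiamine, with no biomarker condition. The Informed Consent Process says that Veterans treated on suspicion will be followed, but only that there may be a follow-up visit.

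The heading of section 4.3 (Aim 3) refers to TD. Its primary outcome compares TDD with non-TDD. Its tests use a TD group made up of Veterans with treatment-responsive TD or with a level outside the laboratory's limits. Its exploratory models take TDD status as the outcome.

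**The concern.** Prevalence is the main result of this study, and 15.1 supports two numerators for it. An analyst working from the primary outcome sentence counts only responders with a low or low-normal level. One working from the endpoint sentence and the TDD definition in the same section counts every responder. The visit 3 rule that would make the two agree is itself stated two ways. Treatment is open label and improvement is a judgement (none or minimal, versus noticeable). If normal-level Veterans are assessed, the choice of definition could therefore be made after the results are known.

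In Aim 3, the tests and the models could use different case groups under one section, so their results could not be read together or tied to the Aim 1 prevalence.

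**Working it through.** **1. The plan's own figures (15.1).** Inputs: 300 enrolled, 15% drop-out, 25% prevalence, an 8-point difference. Section 15.1 states no alpha; two-sided 0.05 is assumed.

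- Evaluable: 300 × 0.85 = 255. The example split is 63 + 192 = 255, and 63/255 = 24.7%, so the TDD count comes from the 25% given for TD.
- Half-width: 1.96 × √(0.25 × 0.75/255) = 5.3 points; at n = 300, 4.9 points. The exact (Clopper–Pearson) half-width at 255 is 5.5. The stated 5.4 is approximately reproduced at 255.
- Power for 25% against 33%: Φ[(0.08 − 1.96 × √(0.25 × 0.75/255)) / √(0.33 × 0.67/255)] = Φ(0.91) = 81.9%, against 81% stated.

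These figures rest on a single 25% count and do not show which definition it belongs to.

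**2. Who is a case under each wording.** The qualifier acute in the TDD sentence is taken to add no further restriction.

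| Veteran | 15.1 primary outcome and Aim 2 | 15.1 TDD sentence | Aim 3 tests |
|---|---|---|---|
| Low level, improves | case | case | case |
| Low-normal level, improves | case | case | case |
| Normal level, improves | not a case | case | case only if treatment-responsive TD needs no biomarker |
| Low level, no improvement | not a case | not a case | case |
| Result lost, improves | cannot be classified | case | unclear |

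The last row arises because section 10.1 keeps the remaining data of treated Veterans whose thiamine values are lost.

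**3. Difference between the two primary counts.** Setting lost results aside, TDD count − TD count = number of normal-level Veterans who are assessed and improve.

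- Visit 3 limited to low or low-normal levels (body of 10.3): the difference is 0.
- All treated symptomatic Veterans assessed (10.3 heading, duration text, data section): the difference is 0 or more, and the documents give nothing from which to derive it.

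The second case is possible in practice. Section 10.2 provides oral thiamine on symptoms around discharge, while results are expected 7 to 10 days after the draw, so some normal-level Veterans may already be on treatment. Section 15.2 also compares levels between responders and non-responders without restricting the range of levels.

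**4. Scale only.** Smallest count that moves the prevalence by more than the stated 5.4 points:

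- Of 255: 13/255 = 5.1; 14/255 = 5.5. For example, 63 to 77 cases is 24.7% to 30.2%.
- Of 300, the denominator 15.1 names: 16/300 = 5.3; 17/300 = 5.7.

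These are thresholds solved back from the precision, not expected counts.

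**5. Aim 3.** The fourth row of the table applies under either visit 3 rule. Such a Veteran is a case in the Aim 3 tests, a non-case in Aim 1, and possibly a non-case in the Aim 3 models. Section 10.2 and Sharing of Results with Participants both foresee Veterans being found by laboratory result alone. No count can be given without assumptions that the documents do not support.

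**The case against.** The best defence is that the study already has a biomarker-based TDD definition. Aim 2 states it, the primary outcome sentence agrees, and the body of 10.3 admits only low or low-normal Veterans to visit 3. The biomarker-free sentence follows directly on the secondary outcomes and could be read as shorthand for them. Of the opposing visit 3 texts, one is a heading, and the consent wording does not promise a visit to everyone treated.

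This narrows the point but does not remove it. The endpoint sentence uses TDD, 15.1 defines TDD without a biomarker and does not refer back to Aim 2, and the duration and data sections plainly state the wider visit 3 rule.

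The objection to Aim 3 largely stands. The aim is declared exploratory, the models are conditional on group size, the tested group is spelled out, and the section heading names TD. A wider biochemical group is a legitimate choice. What remains is that the outcome and the models are stated for a different group.

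A reader might also infer that the Aim 3 tested group is simply broader than the TDD group. The documents do not establish this. If treatment-responsive TD carries the biomarker, as TD does in the primary outcome, normal-level responders are TDD cases under 15.1 but outside the tested group. The two groups then overlap and neither contains the other.

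**Conclusion.** The primary endpoint is wrong as written: one section gives two case definitions for its numerator, and the visit 3 texts that decide whether this matters disagree. It should be settled before analysis.

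A reader might infer that the two counts must differ, or that the reported prevalence will be overstated by some known amount. The documents support neither. The gap may be 0 and cannot be derived; 14 of 255 and 17 of 300 only show what it would take to exceed the stated precision. Nor is the stated power in error, since it reproduces to within about a point under two-sided 0.05.

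The Aim 3 mismatch is real but secondary, and its size is unknown.

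**What to change.** 1. Reconcile section 10.3 (heading and body), Study Duration/Study Timeline, Data and Specimen Banking, and the consent wording on who is assessed at visit 3.
2. Use one case definition for the primary endpoint, the one already in the primary outcome sentence and Aim 2: low or low-normal biomarker and symptoms that improve. Amend the biomarker-free TDD sentence in 15.1, use the same term in Study Endpoints, and say how treated Veterans with lost thiamine results are counted.
3. Report response regardless of biomarker only under 15.2, labelled as distinct from the Aim 1 prevalence, and only if the reconciled visit 3 rule allows it.
4. In Aim 3, use the same named case group for the tests and the models. Label any analysis on the other group as a sensitivity analysis.
5. State that the 25% planning value is given for TD and is assumed for this endpoint.

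The cost is wording and, at most, one sensitivity analysis, with no new data. The downside is that the primary prevalence may be lower than under the biomarker-free wording, with fewer cases for the secondary comparisons. The wording alone will not make the rule fully operational: the documents give no numerical limits for low-normal and do not say which of the two assays must qualify.

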2. Remainder of data stored in the database include the unique study ID, age, sex, race, ethnicity, all lab results (as described in Procedures section 10.1), nutrition screening results (as described in Procedures section 10.2), symptom and function survey (section 10.2) and physical exam findings (section 10.2). For symptomatic veterans who are started on thiamine repletion, the symptom and function survey and physical exam findings will be repeated at visit 3 and recorded in the database.

Paper records of data include:

1. Patient name and hospital room number.
2. All study data will be recorded on paper and stored in locked file cabinets within the locked research department.

Sharing of Results with Participants

Thiamine and other micronutrient results will be shared with Veteran participants and will be available for them to view in their electronic medical record. For Veterans found to have low thiamine levels, we will call the veteran and start them on thiamine tablets if they haven't already been started on them. We will notify their primary care doctor as well to ensure ongoing thiamine repletion after the study has concluded.

Withdrawal of Participants

We do not anticipate withdrawing participants from our study without their consent. Participants may withdraw from the study voluntarily at any time by in person meeting or telephone contact with study managers. The Principal Investigator also reserves the ability to early exit subjects from the study at any time in the event a subject is non-compliant with study visits any other component of the study. This will be exercised at the discretion of the PI only after multiple contact attempts have been made and a certified letter sent to the subject.

Approach to Analysis:

All data will be analyzed by a statistician affiliated with the VA research department trained biostatistician. The data will be analyzed using the statistical software SAS on the VA Informatics and Computing Infrastructure (VINCI).

15.1 Prospective cohort study to determine the prevalence and risk associations of TD.

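### Primary prevalence divides by everyone enrolled, but case status needs a Visit 3 response and no rule covers a missing one, so each true case lost before Visit 3 counts as a non-case

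*Combined protocol and SAP*

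**What the plan says.** **Estimator.** Section 15.1 (Statistical analysis/power calculations) gives the primary endpoint as "the prevalence of TDDs which we will compute as the proportion of TDD cases over the total number of subjects enrolled".

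**Case definition.** Section 15.1 (Measurements) defines TD as "abnormally low or low normal thiamine biomarkers combined with symptoms that respond to thiamine replenishment". Shortly afterwards it defines a TDD by symptoms attributable to TD that improve on thiamine, with no biomarker condition. Aim 2 defines TDDs by a low or low-normal level plus improving symptoms. All three require improvement.

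**When improvement is observed.** Data and Specimen Banking says: "For symptomatic veterans who are started on thiamine repletion, the symptom and function survey and physical exam findings will be repeated at visit 3". Section 10.3 brings back "All Veterans with low biomarkers OR low normal biomarkers and clinical symptoms of TDDs that were initiated on replacement". Under Study Duration, Veterans without TD symptoms finish at Visit 2, before discharge.

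**Expected loss.** Section 15.1 anticipates 15% drop-out: "A sample size of 300 and estimated drop out of 15% leaving 255 subjects would provide us with 81% power". An illustration of prevalence ratios works "with 63 TDD and 192 non-TDD patients". On precision, in per cent: "Such an enrollment would provide us with a precision of TDD prevalence of +/- 5.4". Withdrawal of Participants lets the investigator "early exit subjects from the study at any time in the event a subject is non-compliant with study visits", after repeated contact attempts and a certified letter.

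**Nearest rules.** Section 10.3 repeats an incomplete thiamine course and reschedules the visit. Section 10.1 keeps the remaining data when thiamine results are lost. The withdrawal text states no analysis consequence. None of these classifies a person whose response was never observed.

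**The concern.** The numerator can contain only people seen at Visit 3, while the denominator contains everyone enrolled. With no rule for a missing response, the stated formula in effect imputes non-case to every true case who does not return. That is a one-directional error in the primary estimate, and a larger sample does not reduce it.

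The plan also gives reasons why loss may not be neutral. Symptom-free Veterans are complete in hospital, so loss after discharge falls on possible cases. The Background expects more rehabilitation needs at discharge among those with TDDs, section 10.2 foresees discharges to nursing or rehabilitation facilities, and Visit 3 takes place at the hospital. None of this gives a loss rate.

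At stake are the reported prevalence, the coverage of its interval, and where the result falls against Hypothesis 1 (10 to 25%).

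**Working it through.** **Inputs from section 15.1:** 300 enrolled, 15% drop-out, 255 remaining, expected prevalence 25%, 81% power for an 8-point difference, precision ±5.4%. **Assumed, because not documented:** L, the loss among true cases before Visit 3; s, the share of enrolled who meet the baseline biomarker and symptom criteria; two-sided alpha 0.05.

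**1. The plan's own figures.**
- Power, one-sample test of 25% against 33%: Φ[(0.08 − 1.96·√(0.25·0.75/n)) / √(0.33·0.67/n)]. This gives 81.9% at n = 255 and 87.3% at n = 300. The stated 81% therefore comes from 255.
- Wald half-width, 1.96·√(0.25·0.75/n): 5.3 points at 255 and 4.9 at 300. The stated 5.4 matches neither exactly; the Wald formula gives it at n = 247. The exact method gives 5.5 at 255.

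**2. Bias of cases/enrolled.** Expected estimate = P × (1 − L). At P = 25% there are 0.25 × 300 = 75 true cases. With L = 15%, 75 × 0.85 = 63.75 are seen, and 63.75/300 = 21.25%.

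**3. Coverage.** Observed cases are taken as Binomial(300, 0.25(1 − L)). Enumerating all outcomes gives the chance that the nominal 95% Wald interval contains 25%.

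| L (assumed) | Expected estimate, true 25% | Coverage of 25% | Expected estimate, true 10% |
|---|---|---|---|
| 0% | 25.0% | 94.5% | 10.0% |
| 5% | 23.75% | 90% | 9.5% |
| 10% | 22.5% | 79% | 9.0% |
| 15% | 21.25% | 62% | 8.5% |
| 20% | 20.0% | 41% | 8.0% |

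**4. Hypothesis 1.** At L = 15%, a true value from 25.0% up to 0.25/0.85 = 29.4% has an expected estimate of 25% or less. A true value from 10.0% up to just under 0.10/0.85 = 11.8% has one below 10%.

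**5. Would using only classified participants cure it?** Let attendance be unrelated to response among those meeting criteria, with P = 25% and L = 15%.
- Known cases/(known cases + known non-cases) = 0.25(1 − L)/(1 − sL) = 22.6, 23.0 and 23.9% for s = 40, 50 and 75%. Simulated Wald coverage is about 82, 85 and 92%. It stays low because non-cases settled in hospital are never lost.
- s × (response among those seen) = 25.0% for each s, with simulated coverage of about 95%. Its delta-method variance, with r = 0.25/s, is r²s(1 − s)/300 + s²r(1 − r)/(300·s·0.85). The half-width is 5.1 points at s = 40% and 5.3 at s = 75%. Cases/300 has 1.96·√(0.2125·0.7875/300) = 4.6.

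**6. If attendance is related to response.** Take s = 50% and r = 50%. With 10% of responders and 20% of non-responders lost, the product estimate is 0.5 × 0.45/(0.45 + 0.40) = 26.5%. With the losses reversed it is 23.5%.

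**7. Bounds at L = 15%,** with the same loss in everyone meeting criteria. Lower: 21.25%. Upper: 0.2125 + 0.15s = 27.25, 28.75 and 32.5% for s = 40, 50 and 75%, with 18, 22.5 and 33.75 of 300 undetermined.

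**The case against.** **The 15% is not a loss rate for cases.** This stands. It is the plan's overall drop-out. The 75-mile exclusion, the Visit 3 payment, rescheduling and the contact steps before early exit may all keep loss down. Every size above is therefore conditional on L. These measures do not classify those still missing.

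**Enrolled may loosely mean followed.** Then 21.25% does not arise, but the text says enrolled. A completer denominator would still over-represent non-cases (step 5).

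**Wider definitions exist.** The Background accepts a low biomarker or a response, in someone with symptoms, and section 4.3 is similarly wide. Under the Background rule at 15% loss, a true 25% reads 25 × (1 − 0.15(1 − f)) = 22.2, 23.1 or 24.1% if a share f of 25, 50 or 75% of cases has a low level (assumed). That is a smaller bias. However, section 15.1 states the primary outcome, and it requires response.

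**A reader might infer that 255 against 300 is an error, or that 63 cases may be reported as either 63/255 = 24.7% or 63/300 = 21.0%.** The document does not support this. Powering on a number reduced for drop-out is normal, the 63/192 split is only a worked example for prevalence ratios, and the stated estimator allows one denominator.

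**The shift is modest.** At 15% loss it is 3.75 points, below the stated ±5.4, and 21.25% is inside Hypothesis 1. This is fair as to severity. But an interval reflects sampling error only, and coverage of 62% shows what a bias of that size does to it.

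**Conclusion.** The concern holds. Read as written, the primary estimator counts every true case without a Visit 3 response as a non-case, and from this source alone it is biased low by the factor (1 − L). Loss of 5 to 20% among true cases would cost 1.25 to 5 points at a true 25%. It rests on two things: response is required for case status, which section 15.1 states, and some true cases are lost, which the plan's drop-out figure makes likely but does not quantify.

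A reader might go further and conclude that the study will under-report prevalence overall, or that its main message is at risk. Neither follows. Improvement is judged open label and without a control group, which could push the estimate the other way, so the net direction is not established. At every loss rate considered, a true 10% still reads 8% or more, well above the 3% quoted for the general population.

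This should be fixed before the data are analysed. It does not invalidate the design.

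**What to change.** 1. **State one case definition for the primary endpoint.** Reconcile the TD definition in section 15.1 (biomarker plus responsive symptoms), the TDD definition there (no biomarker) and Aim 2, and say whether either assay suffices. If no biomarker is required, section 10.3 and Study Duration must also agree on whether symptomatic Veterans with higher levels attend Visit 3.

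2. **Replace the denominator sentence with:** *Primary prevalence = (proportion of enrolled participants with known baseline status who meet the baseline criteria) × (proportion responding among those who meet the criteria and have a Visit 3 response), with a 95% CI by the delta method or bootstrap.* Equivalently, weight Visit 3 attenders by the inverse of attendance among those meeting criteria, within baseline biomarker and symptom strata where numbers allow.

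3. **Always report both bounds over all enrolled,** with the number undetermined at each stage. Counting all undetermined as non-cases gives the current cases/enrolled figure; counting all as cases gives the upper bound.

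4. **State the n and interval method behind ±5.4%.**

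**Cost:** a paragraph of text and short code, with no new data or visits. At 15% loss, with 40 to 75% meeting criteria, the half-width is about 5.1 to 5.3 points against 4.6. The estimate assumes that attendance is unrelated to response given baseline status. The bounds show how far the result could move if that fails.
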